#### 7.3.4 SAE Reporting Timelines

All SAEs, whether or not they are suspected to be related to study treatment, are to be reported within 24 hours after recognition of the event.

To report the SAE, the SAE form needs to be completed electronically in the electronic data capture (EDC) system for the study without delay and within 24 hours of awareness. When the form is completed, the Medpace Safety personnel will be notified electronically by the EDC system and will retrieve the form. If the EDC system cannot be accessed, either an email needs to be sent to Medpace Safety at [REDACTED] or the Medpace SAE hotline (phone number listed below) has to be called, and the completed paper SAE form has to be faxed/mailed to Medpace (fax number listed below) without delay and within 24 hours of awareness. A confirmation of the submission of the SAE form has to be filed in the investigator study file. When the EDC system becomes available, the SAE information must be entered within 24 hours of the system becoming available.

Safety Contact Information:

Medpace Clinical Safety

E-mail: mailto:[REDACTED]

Medpace SAE hotline – USA:

Telephone: [REDACTED]

Facsimile: [REDACTED]

Medpace SAE hotline – Europe:

Telephone: [REDACTED]

Fax: [REDACTED]

## Follow-Up Reports

The Investigator must continue to follow the subject until the SAE has subsided or until the condition becomes chronic in nature, stabilizes (in the case of persistent impairment), or the subject dies.

Within 24 hours of receipt of follow-up information, the Investigator must update the SAE form electronically in the EDC system for the study and submit any supporting documentation (e.g. subject discharge summary or autopsy reports) to Medpace Clinical Safety via fax or e-mail to ensure continuous safety monitoring. If it is not possible to access the EDC system, refer to the procedures outlined above for initial reporting of SAEs.

All SAEs, whether or not they are suspected to be related to study treatment, will be submitted by Medpace Clinical Safety to:

## Waivers from SAE Reporting Requirement

The following exceptions are not considered SAEs for this study:

- hospitalizations due to infusions on consecutive days (e.g. for patients with long travel hours);
- surgeries that are elective or were planned before study entry;
- prolongation of existing hospitalizations for non-medical reasons.

The sponsor/designee will report all relevant information about suspected unexpected serious adverse reactions (SUSARs) that are fatal or life-threatening as soon as possible to the FDA and all applicable European competent authorities in all participating countries concerned as well as to the IRB/IEC and in any case no later than seven days after knowledge by the sponsor/designee of such a case. Relevant follow-up information will subsequently be communicated within additional eight days.

All other SUSARs will be reported to the FDA and all applicable European competent authorities in all participating countries concerned as well as to the IRB/IEC as soon as possible but within a maximum of 15 days of first knowledge by the sponsor/designee.

The sponsor/designee will also report any additional expedited safety reports required in accordance with the timelines outlined in country-specific legislation. The sponsor/designee will also inform all investigators as required per local regulation.

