Cognitive behavior therapy (CBT) including exposure and response prevention, and selective serotonin re-uptake inhibitors (SSRIs) are the primary evidence-based therapies for OCD [10, 11]. Approximately 50%–80% of patients with OCD respond to these treatments, but a substantial proportion of patients subsequently experience lifelong treatment resistance [12]. Behavioral interventions, such as habit reversal training, and psychopharmacological treatment strategies are the recommended treatments for tic disorders [13]. In contrast to the recommended treatments, when an infectious or autoimmune etiology is suspected, these treatments for OCD and tics may be insufficient.

Supplemental or alternative treatment options when suspecting PANDAS include antibiotics or tonsillectomy to treat and/or prevent GAS infection [14]. To suppress the immune system in patients with putative autoimmune-based OCD, corticosteroids [15], therapeutic plasma exchange [16, 17], IVIG [17], or anti-CD20 monoclonal antibodies (rituximab) [15] have been given. Administration of non-steroidal anti-inflammatory drugs (NSAIDs) to ameliorate psychiatric symptoms of PANS also has been suggested and is in line with the autoimmune etiology theory [18]. A consortium of clinicians and researchers have authored three consensus papers regarding treatment of PANS using psychiatric and behavioral interventions [19], immunomodulatory therapies [20], and antibiotics [21]. These guidelines of the clinical management of PANS are based on clinical experience and on research, and support use of immunomodulatory treatment and antibiotics, beside standard psychiatric treatment. A

systematic review on the management of PANS and related disorders identified 12 studies involving the following treatments: penicillin, azithromycin, IVIG, plasma exchange, tonsillectomy, CBT, NSAIDs, and corticosteroids [12]. A further 65 case reports in which patients received immunomodulatory treatments, antibiotics, and/or psychotropics were identified [12]. Research on PANS treatment (and related disorders) is scarce, and further investigation is needed in which treatment strategies are rigorously investigated.

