### **7.3.2.2 Collection of AEs**

Adverse events will be collected throughout the study from the date of informed consent until the last study visit (end of study) and SAEs will be collected a further four weeks after last IMP dose if the site becomes aware of the event (no proactive monitoring).

The condition of the patient will be monitored throughout the study from the moment that informed consent has been given. During each visit, whether scheduled or unscheduled, AEs will be elicited using a standard non-leading question such as "How have you been since the last visit/during the previous study period?" Adverse events should be collected from the moment that informed consent has been given and at each subsequent visit.

Any AE or ADR which occurs during the study will be noted in detail in the appropriate pages of the eCRF. If the patient reports several signs or symptoms representing a single syndrome or diagnosis, the diagnosis should be recorded in the eCRF. The investigator will grade the severity of all AEs or ADRs (mild, moderate, or severe), the seriousness (non-serious or serious), and the causality as defined in Sections 7.3.2.3, 7.3.3, and 7.3.2.4. The Sponsor is responsible for assessing the expectedness of each ADR (expected or unexpected) as defined in Section 7.3.2.5.

In the event of clinically significant abnormal laboratory findings, the tests will be repeated as deemed necessary by the treating physician and the patient followed up until the laboratory values have returned to normal and/or an adequate explanation for the abnormality has become available.

Diseases, signs and symptoms, and/or laboratory abnormalities already present before informed consent will not be considered AEs unless an exacerbation in intensity or frequency (worsening) occurs.

Fluctuations of PANS/PANDAS symptoms will not be considered untoward medical occurrences and will not be reported as AEs if the investigator deems them to be within the expected range of normal symptom fluctuation or if they do not require concomitant medications or procedures.

The investigator will provide detailed information about any abnormalities and about the nature of and reasons for any action taken as well as any other observations or comments that may be useful for the interpretation and understanding of an AE or ADR.

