#### **7.3.3 Serious Adverse Events (SAEs)**

A **serious AE (SAE)** is any untoward medical occurrence that at any dose:

- results in death,
- is life-threatening (see below),
- requires hospitalization or prolongation of existing hospitalization,
- results in persistent or significant disability/incapacity,
- is a congenital anomaly/birth defect,
- is another important medical event.

**NOTE:** The term 'life-threatening' refers to an event in which the patient was, in the view of the reporting investigator, at immediate risk of death at the time of the event; it does not refer to an event which may hypothetically have caused death had it been more severe.

In deciding whether an AE/ADR is serious, medical judgment should be exercised. Thus, important AEs/ADRs that are not immediately life-threatening or do not result in death or hospitalization but may jeopardize the patient or may require intervention to prevent one of the other outcomes listed in the definitions above should also be considered serious.

In addition, although not classified under the seriousness criteria, all suspected transmissions of an infectious agent should be reported as SAE. A suspected virus transmission means that virus antigen has been detected in the patient. A passive transmission of antibodies alone does not constitute a suspected virus transmission.

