11.1. Adverse Events

All reported AEs will be coded according to MedDRA.

All AEs with first onset or worsening during the treatment period, i.e. after first IMP administration, are accounted for in the analysis.

In general AE frequency tables will feature columns for each treatment group (as defined in section 8.4) and a total column in a side-by-side fashion.

All reported events will be listed and tabulated in full detail; in particular the following key figures will be presented:

- Total number of AEs reported by severity and overall
- Number of related AEs by severity and overall
- Number of TEEs and HTRs
- Number of SAEs
- Number of AEs leading to withdrawal
- Infusional AEs (AEs that occur during or within: (a) 1 hour, (b) 24 hours, and (c) 72 hours following an infusion, regardless of other factors that may impact the causality assessment

Narratives will be prepared describing each death, other SAEs, and other significant AEs that are judged to be of special interest because of clinical importance, including all TEEs and HTRs reported.

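### The SAE waiver for elective or pre-planned surgery has no new-onset or worsening limit, so a hospital operation for an on-study problem can drop out of the SAEs

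*Protocol*

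**What the plan says.** Protocol Section 7.3.3 sets the general rule: an untoward occurrence that "requires hospitalization or prolongation of existing hospitalization" is serious. Section 7.3.4 says that SAEs, related or not, "are to be reported within 24 hours after recognition of the event".

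The list headed Waivers from SAE Reporting Requirement then opens with "The following exceptions are not considered SAEs for this study". It has three items: hospital stays caused by infusing on two consecutive days, "surgeries that are elective or were planned before study entry", and longer stays for non-medical reasons.

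For conditions that predate informed consent, Section 7.3.2.2 says that they "will not be considered AEs unless an exacerbation in intensity or frequency (worsening) occurs". The surgery waiver has no such clause.

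SAP 11.1 lists "Number of SAEs" among its key safety figures and provides a narrative for every SAE. The legible SAP text neither redefines an SAE nor narrows the waiver.

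**The concern.** A waiver of this kind normally keeps out admissions that say nothing about the study drug, such as an operation already booked for a stable, long-standing problem. This bullet reaches further, because it rests on how the surgery was scheduled and not on when or why the need arose. The other two waivers are tied to a non-medical reason; this one is not.

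The lead-in also does more than lift a reporting duty: it says that the listed items are not SAEs. An affected event would therefore miss the 24-hour report, the SAE count and the automatic narrative. Assessment as a suspected unexpected serious adverse reaction also depends on the event being serious.

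The situation can arise in this trial. Protocol Section 1 notes that "treatment options when suspecting PANDAS include antibiotics or tonsillectomy to treat and/or prevent GAS infection", and Section 1.1 reports that multiple children acquired new group A streptococcal infections during the earlier placebo-controlled IVIG trial. Up to 30 centers are planned, and two of them could classify the same admission differently, one by Section 7.3.3 and the other by the waiver.

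**Working it through.** No arithmetic applies. The check reads the waiver against the AE and SAE definitions and then sorts the possible cases.

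**Step 1: grammar of the bullet.** The phrase is "surgeries that are elective or were planned before study entry". It has two verbs and so two separate alternatives. The time limit belongs only to the second. Elective surgery is therefore waived whenever the need for it arose, and neither alternative mentions new onset or worsening.

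**Step 2: comparison with the neighbouring rules.**
- Section 7.3.3 makes an occurrence needing hospitalization serious. The waiver takes elective or pre-planned surgical admissions out of that rule.
- Section 7.3.2.2 turns a pre-existing condition into an AE once it worsens, but that decides AE status, not seriousness. Nothing carries the worsening test over to the waiver.
- Section 7.3.3 leaves other routes to seriousness, including medical judgment for events that "may require intervention to prevent one of the other outcomes listed in the definitions above should also be considered serious".
- Section 7.3.5 requires thromboembolic events and hemolytic transfusion reactions to be reported as SAEs, whatever procedure follows.
- Section 7.3.2.1 has a category of other significant AEs, which includes those leading to an intervention.

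**Step 3: the cases.**

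| Case on study | Result as written |
|---|---|
| Elective surgery in hospital for a new or worsened condition, not of special interest, hospitalization the only criterion | Waived; AE only |
| Surgery arranged before entry, condition then worsens, hospitalization the only criterion | Surgery waived; the worsening is an AE only |
| Surgery neither elective nor arranged before entry, with hospitalization, for an on-study problem | Not waived; SAE |
| Thromboembolic event or hemolytic transfusion reaction followed by any surgery | Event still reported as an SAE |
| Underlying condition meets another seriousness criterion, or is judged serious | Still an SAE |
| Elective surgery for a pre-existing condition that has not worsened | Waived, in line with Section 7.3.2.2 |

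The gap is the first two rows. The last row is the legitimate use of the waiver.

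**The case against.** **A stated exception does not contradict the rule it qualifies.** This stands. The text is headed as waivers and introduced as exceptions, so the problem is the scope of the exception and its fit with Sections 7.3.2.2 and 7.3.3.

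**The bullet names the procedure, not the condition.** This stands in part. A new or worsened condition remains an AE, may be an other significant AE, and can be serious on another criterion or by medical judgment. SAP 11.1 lists and tabulates all reported events, and gives a narrative to other significant AEs judged clinically important. But these routes need a different criterion or someone's discretion. Because the other two bullets waive hospital stays, a site can readily read this one as waiving the surgical stay too.

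**The scenario is narrow.** This also stands. Tonsillectomy appears as background, not as a study procedure. The documents do not say that it would be elective or need admission, and the operation would have to fall within two nine-week phases or the short SAE follow-up.

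**Safety is exploratory, its analysis descriptive, and the waiver the same in both arms.** True. A reader might infer that the Panzyga-placebo comparison is biased. The documents show no differential effect, so that inference is not supported.

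**Conclusion.** The point holds in limited form. An elective or pre-planned hospital operation for a condition that arose or worsened on study can be lost as an SAE if the condition is not of special interest and hospitalization is its only seriousness criterion. This rests on reading the two alternatives as separate, which is what the wording says, and on finding no text elsewhere in the legible documents that narrows them.

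Two stronger readings are tempting and do not hold:
- That every hospital operation for an on-study problem escapes SAE reporting. Surgery that is neither elective nor pre-planned is not waived, other seriousness criteria still apply, and thromboembolic events and hemolytic transfusion reactions are always reported as SAEs.
- That the SAE count is understated by some percentage. The documents give no rate of elective surgery and no expected number of SAEs, so any percentage would rest on invented counts.

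The size of the effect therefore cannot be stated. The primary efficacy analysis is unaffected. It is still worth correcting: followed exactly, the rule removes an admission that Section 7.3.3 would make serious, and the correction is small.

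**What to change.** Reconcile the waiver with Sections 7.3.2.2 and 7.3.3 by rewording the bullet along these lines: *elective or pre-planned surgeries for a condition that was present before informed consent and has not worsened since*. Surgery for a new or worsened condition is then assessed for seriousness under Section 7.3.3 like any other event.

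Keep the word elective. Without it, elective surgery scheduled after entry for a stable pre-existing condition would lose its waiver, although Section 7.3.2.2 does not treat that condition as an AE. The new-onset and worsening qualifier is enough.

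The cost is one line in a protocol amendment, the matching line in the sites' SAE completion guidance, and a few more SAE forms. No new data or procedures are needed, and SAP 11.1 can stay as it is.

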### 7.3.5 Adverse Events of Special Interest (AESI)

The following AEs are defined as AESI:

- thromboembolic events (TEEs);
- hemolytic transfusion reactions (HTRs).

For these AESI, the general definitions and procedures that are described in Section 7.3 also apply. These AESI must be reported as SAEs as described in Section 7.3.4.

### 7.3.5.1 Thromboembolic Events (TEEs)

There is clinical evidence of an association between IVIG administration and TEEs [22], such as ischemic stroke, transient ischemic attack, cerebral infarction, cerebrovascular accident, cerebral thrombosis, embolic infarctions, [acute] myocardial infarction, deep vein thrombosis, pulmonary embolism, venous thrombosis.

As a component of the assessment of AE, the investigator will be questioned regarding the occurrence of TEEs. These are defined according to the Standardized Medical Dictionary for Regulatory Activities query (SMQ) "Embolic and thrombotic events". Thromboembolic events will be reported as SAEs. All TEEs must also be recorded in the AE page of the eCRF. If TEEs are suspected at any time during the study, appropriate examinations according to local standards should be performed (e.g. Doppler scan using color duplex, X-ray) and the results documented. Therapeutic measures managing suspected TEEs shall be initiated according to local clinical practice (e.g. anticoagulation).

### 7.3.5.2 Hemolytic Transfusion Reactions (HTRs)

Hemolytic transfusion reactions can develop subsequent to IVIG therapy; IVIG-related hemolysis is associated with passive transfer of anti-A and anti-B hemagglutinins. Hemolytic transfusion reactions will be reported as SAEs.

Hemolytic transfusion reactions will be monitored at each visit (see Flow Chart of Assessments).

The results of these additional tests and any clinical signs or symptoms potentially related to hemolysis will be documented in the patient's medical record.

Therapeutic measures managing suspected HTRs shall be initiated according to local clinical practice.

### 7.3.6 Laboratory Tests

The following laboratory parameters will be investigated during the study at the time points specified in Section 6.

### 7.3.7 Viral Safety Tests

Without NMR

### 7.3.8 Vital Signs and Physical Examination

11. **What is the primary purpose of the proposed system?**

12. **What are the key features of the proposed system?**

13. **How will the proposed system be implemented?**

14. **What are the potential challenges and risks associated with the proposed system?**

15. **What is the timeline for the proposed system?**

16. **What is the budget for the proposed system?**

17. **What is the expected outcome of the proposed system?**

18. **What is the proposed system's impact on the organization?**

19. **What is the proposed system's impact on the industry?**

20. **What is the proposed system's impact on society?**

It is the investigator's responsibility to review all vital sign findings. Medical and scientific judgment should be exercised in deciding whether an isolated vital sign abnormality should be classified as an AE.

If a clinically significant vital sign abnormality is a sign of a disease or syndrome (e.g. high blood pressure), only the diagnosis (i.e. hypertension) should be recorded in the Adverse Event eCRF.

Physical examinations will be performed at the visits specified in Section 6.1.

A series of eight horizontal black bars of varying lengths, decreasing in length from left to right. The bars are evenly spaced and extend across the width of the frame.

Targeted physical examinations should be limited to significant medical conditions identified at Screening. Changes from baseline abnormalities at subsequent visits should be recorded in patient notes. New or worsened clinically significant abnormalities should be recorded as AEs in the Adverse Event eCRF.

### 7.3.9 Other Relevant Safety Information

#### a. *Post-study related safety reports*

Any SAE which occurs up to four weeks after the last IMP administration should be reported by the investigator to the Sponsor in case the investigator becomes aware of it (see Section 7.3.4). Proactive monitoring for post-study SAEs is not required.

In case a post-study SAE is identified, the investigator should complete an SAE form and also state the relation to the clinical study in the report.

Deaths occurring within four weeks after the last IMP administration should also be reported, regardless of whether or not they are considered treatment-related.

#### b. *Pregnancies*

Clinical experience with immunoglobulins suggests that no harmful effects are to be expected on the course of pregnancy, or on the fetus and the neonate, or on fertility. As such, no contraception measures are needed for male subjects with a pregnant or non-pregnant WOCBP partner.

Every effort will be made to avoid a pregnancy during the use of an IMP. For WOCBP, if the patient is unwilling to use a protocol-recommended method of contraception from Screening throughout the study treatment period and for four weeks following the last dose of study drug, this constitutes an exclusion criterion. Pregnancies occurring during the study (fetal exposure to the IMP) need to be reported. Women of childbearing potential using an acceptable effective contraceptive method during the study will be enrolled. Pregnancy tests will be completed at Screening. A WOCBP is defined as a fertile woman, from the beginning of menstruation, unless permanently sterile. A man is considered fertile after puberty unless permanently sterile by bilateral orchidectomy.

Acceptable effective contraceptive measures include the following:

- combined (estrogen- and progestogen-containing) hormonal contraception associated with inhibition of ovulation (oral, intravaginal, transdermal)
- progestogen-only hormonal contraception associated with inhibition of ovulation (oral, injectable, implantable)
- progestogen-only oral hormonal contraception, where inhibition of ovulation is not the primary mode of action
- intrauterine device
- intrauterine hormone-releasing system
- bilateral tubal occlusion

- vasectomized partner
- sexual abstinence
- male or female condom with or without spermicide
- cap, diaphragm or sponge with spermicide

In case of pregnancy during the study, the investigator should complete the Pregnancy Notification Form and send or fax it to Medpace within 24 hours of becoming aware of the pregnancy (see Section 7.3.4).

Follow-up information on the outcome of both mother and fetus will be requested by a Sponsor representative.

